9.0. RANDOMIZATION & STUDY DRUG ADMINISTRATION

9.1. Randomization: After initial assessments, participants are randomized to double-blinded Phase 1 drug assignment (escitalopram or placebo). As our primary interest for Phase 1 is related to escitalopram response, we will allocate participants in a 2:1 drug-to-placebo ratio. Randomization will be conducted by the Vanderbilt Investigational Drug Service. Nondepressed individuals will not be randomized to study drug.

Randomization will be stratified by MRI measures of total cerebral WML volume. Our measurement of total WML volume is automated and available within 24 hours of the scan and subjects will be stratified as "high" or "low" total cerebral WML volume. Based on pilot data, we will use a cutoff of 3.86mL; this is the median 3T WML volume from a cohort of 145 depressed elders analyzed using our WML segmentation method. When we reach 50% enrollment, we will re-assess this cutoff based on study data and adjust if necessary.

If there are delays in scan processing, stratification will be determined using the Coffey-modified Fazekas visual rating scale (2), dichotomizing participants as "high" (2 or 3, confluence of foci) or "low" (0 or 1, absent or punctate foci).

MRI measures will only be used for stratification. They will not guide or determine treatment decisions.

9.2. Phase 1: Blinded Escitalopram or Placebo: We selected escitalopram due to its tolerability, ease of dosing, and lack of effects on dopamine and norepinephrine (115). The Vanderbilt IDS will prepare over-encapsulated escitalopram and matching placebo and maintain the blinded assignment in case of emergencies. Participants will receive one tablet (10mg or placebo) for at least 2 weeks. If tolerated, it can be increased to a target dose of two tablets (20mg) daily at the two-week study contact, but dosing changes will not be made at week 6 or later. For problems with tolerability, the dose can be reduced to the previous level, but not below one tablet daily.

9.3. Transition: After 8 weeks subjects will be assessed for remission (MADRS \leq 7). Those achieving remission will end their study participation. Those who are not remitted will have their Phase 1 drug tapered over a week to decrease the chance of discontinuation syndrome then progress to Phase 2.

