This approach will slightly differ for each study phase. For Phase 1, models will include drug arm (placebo or escitalopram). To examine for differences in how tract impairment affects remission in each arm, we will test for interactions between drug assignment and tract integrity (WML & FC). We will explore significant interactions in individual models. For subjects entering Phase 2, we will test for differences in tract integrity (WML & FC) between those originally assigned to escitalopram and placebo. If differences are observed, in models we will control for original Phase 1 cohort assignment. In exploratory models, we will use similar approaches to test for the additional effect of cognitive domain function (Table 5) on remission. We will also use this approach for Exploratory Aim 2 when we examine the effect of connectivity deficits in other tracts.

Importantly, the relationship between connectivity and antidepressant response may not be linear. It is possible that a ‘threshold’ must be crossed in order for tract connectivity deficits to influence response (3). To properly take into account nonlinear effect of a continuous predictor variable (e.g., WML, FC) on response variable (e.g., remission or nonremission) in the models, we will employ restricted cubic splines of the predictor. Statistical significance of the nonlinear terms via F-test implies that the relationship between the two measures of interest can be nonlinear.

15.1. Sample Size and Statistical Power:

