Aim 1: From our published report (129) correlations of the FC of the PFC with the amygdala and the hippocampus were in the range of 0.52 to 0.55. A sample of 130 subjects, will have > 90% statistical power for associations ≥ 0.30 (two-tailed $\alpha = 0.05$). However, our primary approach to the analysis of Aim 1 will use canonical correlation with no known powering algorithms; sample size and effect estimates are used to guide the appropriateness. Using the multiple regression approach (single dependent) as a conservative estimate, a sample size of 130 achieves 83% statistical power to detect an R^2 as small as 0.06 (standardized beta = 0.20, 6% shared variance) attributed to the association of WML with a significance level (alpha) of 0.05 after adjusting for other proposed covariates. These calculations assume that the variables for which we are adjusting have an R^2 of 0.10 (10%) (130). We suspect that the control variables will have a higher inter-correlation value, thus increasing our power for testing the effect of a single variable.

Aim 2: The study includes a placebo arm to identify effects specific to an active depressant while having a comparable number of subjects receiving each active drug. Powering the study for Phase 1, Table 2 presents estimates for our proposed sample size using unadjusted effects of low vs. high WML values on the respective

outcomes of interest found in our preliminary data. The logistic regression approach allows for the testing of effects adjusted for known covariates. Using this approach, assuming a base non-remittance rate of 0.36 (36%), a sample size of 130 will enable us to detect a log hazard ratio as small as 0.45 for a specific measure. We conservatively included an assumption that covariates would account to up to 10% share of the effect on nonremission. If that value is less, our statistical power will increase for the same hazard ratio. Using high vs. low tract WML volume as an example, after controlling for other effects, our sample will enable us to detect an effect on the likelihood of non-remittance of at least 25% (high WML vs. low WML, $0.45 / 0.36 = 1.25$ or 25% increase). Continuous as well as nonlinear operationalization of effects will be examined.

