16.0 PRIVACY AND CONFIDENTIALITY

Protocol Version: 2.0

Protocol Date: 04/10/2020

Region	Low WML	High WML	Power ($\alpha = 0.05$)
Baseline MADRS			
• UF, R	21.0 (12.2)	29.5 (3.0)	0.98
• ATR, R	17.4 (8.6)	29.7 (9.0)	1.00
3-Month MADRS			
• Ant. CB, L	8.8 (7.0)	14.8 (5.8)	0.99
• Post. CB, R	7.7 (7.6)	14.6 (7.8)	0.99
• Post. CB, L	5.2 (2.9)	16.0 (7.6)	1.00

Confidentiality Procedures: As the PI, [name] will assure all procedures protecting study data designed to guard subject confidentiality conform to the Vanderbilt Human Research Protection Program requirements. Additionally, the Vanderbilt IRB must approve all procedures and safety precautions before the study can begin. All non-electronic data (clinical evaluations, paper assessments) will be stored securely in locked offices or laboratories accessible only by study staff. All electronic data will be stored in secured servers with limited access. RedCAP will be used for data management.

Further, all information that could potentially directly identify a subject is removed from all study data. This includes MRI data, electronic and paper assessments. Direct identifiers will be replaced with a unique four-digit code. The key to linking the code to subject identity will be kept separately from study data, in a locked file in password-protected computer in [name] office. Only study staff involved in clinical recruitment and assessment will have access to individually identifiable private information. All other study staff, including image analysts, will be blinded to subject identity and will only have access to the coded identifier.

Privacy Procedures: Informed consent and all study procedures will occur in private research offices and private research examination rooms.

17.0 FOLLOW-UP AND RECORDS RETENTION:

Study records will be maintained for at least six years after the study is closed with the IRB. After that time, study data may be destroyed or anonymized, meaning all links to direct identifiers will be destroyed. Any study data in the medical record will be kept indefinitely.

LITERATURE CITED

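### Table 2's Phase 1 power (0.99 to 1.00) is for a difference in mean 3-month MADRS; the drug-by-tract interaction that tests Hypothesis 3 on 8-week remission has no stated power, and probably much less

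*Combined protocol and SAP*

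**What the plan says.** Section 15.1 (Aim 2) opens the Phase 1 justification with "Powering the study for Phase 1, Table 2 presents estimates for our proposed sample size using unadjusted effects of low vs. high WML values", and describes these effects as coming from preliminary data. The table, identified by its content because it carries no caption, gives mean (SD) MADRS for low and high WML groups. Two rows are under "Baseline MADRS" (power 0.98 and 1.00). Three are 3-month MADRS rows for the CB (power 0.99, 0.99, 1.00). It has no remission outcome, treatment arm or interaction, and no post-treatment row for the uncinate fasciculus or for functional connectivity, both of which Hypothesis 3 also names.

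Section 15.1 then turns to a covariate-adjusted logistic model for non-remission, with a base rate of 0.36. It says that "a sample size of 130 will enable us to detect a log hazard ratio as small as 0.45 for a specific measure" and assumes that "covariates would account to up to 10% share of the effect on nonremission". It attaches no power to that statement.

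On the planned test, section 9.3 says "After 8 weeks subjects will be assessed for remission", and sections 8.1.a and 15.0 define remission as MADRS of 7 or less. Section 9.1 allocates 2:1 to escitalopram. For Phase 1, section 15.0 says "we will test for interactions between drug assignment and tract integrity (WML & FC", in models adjusted for baseline MADRS, age, sex and vascular risk. Hypothesis 3 expects tract damage to predict non-remission on escitalopram but not on placebo.

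**The concern.** The power offered for Phase 1 belongs to a different quantity from the one Phase 1 tests. It concerns a mean rather than a proportion, 3 months rather than 8 weeks, an unadjusted rather than an adjusted effect, and a single pooled contrast rather than a difference between arms.

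The last of these matters most. Section 15.1 says the placebo arm is there to isolate effects specific to active drug, and section 12.0 (item 4) defends the 2:1 ratio on the ground that predictors should differ between arms. The interaction is the test of that difference. A null WML result in about 43 placebo participants cannot establish it alone.

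If a reader carries 0.99 over to the interaction, a non-significant result would look like good evidence that WML acts the same way under drug and placebo. At the power found below, it would say little either way.

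**Working it through.** **Inputs from the documents.** 130 evaluable participants (section 4.0). The 2:1 ratio gives 130 × 2/3 ≈ 87 on escitalopram and 43 on placebo. Table 2 mean (SD), low then high WML: Ant. CB L 8.8 (7.0), 14.8 (5.8); Post. CB R 7.7 (7.6), 14.6 (7.8); Post. CB L 5.2 (2.9), 16.0 (7.6). Alpha is 0.05.

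**Assumptions not in the documents.** Two-sided tests; equal high/low split; normal MADRS; 3-month effects present in full at week 8; no WML effect on placebo; placebo non-remission of 0.5 to 0.8.

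**Step 1. Reproduce Table 2.** SD = √((SD₁² + SD₂²)/2), d = difference/SD, power ≈ Φ(d√(n/2) − 1.96).

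- Ant. CB L: SD = √((49.00 + 33.64)/2) = 6.43 and d = 6.0/6.43 = 0.933. With 43 per group, Φ(4.33 − 1.96) = 0.991 (noncentral t 0.990).
- Post. CB R: d = 6.9/7.70 = 0.896, giving 0.986 (t 0.984).
- Post. CB L: d = 10.8/5.75 = 1.878, giving 1.000.

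With 65 per group all three are 0.999 or more. The stated 0.99, 0.99 and 1.00 are therefore sound for a difference in means.

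**Step 2. Convert to non-remission.** P(MADRS > 7), using a cut of 7.5, is 1 − Φ((7.5 − mean)/SD).

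| Row | Low WML | High WML | Log odds ratio |
|---|---|---|---|
| Ant. CB L | 0.574 | 0.896 | 1.856 |
| Post. CB R | 0.510 | 0.819 | 1.465 |
| Post. CB L | 0.214 | 0.868 | 3.188 |

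**Step 3. Remission within escitalopram, about 43.5 per WML group.** A two-proportion test has power of about 0.94, 0.87 and 1.00. A Wald test of the log odds ratio has 0.89, 0.84 and 1.00.

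**Step 4. Arm-by-WML interaction on remission.** Variance = Σ 1/(n p(1 − p)) over four cells, with 43.5 per escitalopram cell and 21.5 per placebo cell. Power ≈ Φ(log odds ratio/√variance − 1.96). The two placebo cells contribute 2/(21.5 p(1 − p)), which is 0.372, 0.409 and 0.581 at p = 0.5, 0.65 and 0.8.

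| Row | Escitalopram variance | Power at 0.5 | at 0.65 | at 0.8 |
|---|---|---|---|---|
| Ant. CB L | 0.341 | 0.59 | 0.57 | 0.49 |
| Post. CB R | 0.247 | 0.46 | 0.44 | 0.36 |
| Post. CB L | 0.338 | 0.97 | 0.96 | 0.91 |

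For example, Ant. CB L at 0.65: √(0.341 + 0.409) = 0.866, and Φ(1.856/0.866 − 1.96) = 0.57. A placebo rate of 0.36 lies inside the range, because 0.36 × 0.64 is the same product as at 0.64.

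**Step 5. Continuous WML predictor.** Simulations (1,500 runs) used a normal WML measure matched to the Table 2 mean differences and pooled SD. Interaction power was about 0.61, 0.61 to 0.64, and 0.99 to 1.00. Splitting the same simulated data at the median gave about 0.43 to 0.44, 0.43 to 0.46, and 0.93 to 0.94.

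**Step 6. Same interaction on continuous MADRS.** SE = √((SD₁² + SD₂²)/43.5 + 2SD²/21.5). Ant. CB L: √(1.900 + 3.844) = 2.40, and Φ(6.0/2.40 − 1.96) = 0.71. Post. CB R: Φ(6.9/2.87 − 1.96) = 0.67. Post. CB L: above 0.99.

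**Step 7. The plan's own 0.45.** The documents do not fix its scale. Read as a log odds ratio per SD, with non-remission 0.36 in both arms and no covariate adjustment, the interaction SE is √(1/(87 × 0.2304) + 1/(43 × 0.2304)) = 0.388 and power is 0.21 (0.195 with the 10% covariate share). Read as a high-versus-low effect, interaction power is about 0.07 to 0.10.

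**The case against.** The strongest reply is that Table 2 is not the plan's only word on Phase 1. Its effects are labelled unadjusted and preliminary, and the logistic passage that follows does address non-remission with covariates. That stands: remission and adjustment are not ignored. But the passage states no power, names no arm and covers no interaction. It also uses 0.45 as a log hazard ratio in a logistic model and then as a rate, dividing it by 0.36 to obtain 1.25.

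A second reply is that section 9.1 places the main Phase 1 interest in escitalopram response, and that dichotomising in 87 people costs little. Step 3 supports this if the pilot effects are real. A reader might infer that Phase 1 as a whole is underpowered, or that Table 2 is miscalculated. The documents support neither: the figures reproduce, and the clear gap is the interaction. Nor do they say whether the pilot participants behind Table 2 were all treated. The two baseline rows bear on Aim 1.

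Third, the figures in Step 4 depend on the model. The plan also uses continuous and spline terms, which do better than a split. The normal conversion implies average escitalopram non-remission of about 0.74, 0.66 and 0.54, against the plan's 0.36, and in two rows it puts 10% to 16% of low-WML scores below zero. These are good reasons to report a range. They do not bring the first two rows to 0.80.

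**Conclusion.** The point holds in limited form. The 0.99 to 1.00 offered for Phase 1 is valid for an unadjusted mean MADRS contrast at 3 months and cannot be carried to the planned test of drug specificity, for which the plan gives no power. With the pilot effects taken in full, interaction power on remission is about 0.49 to 0.59, 0.36 to 0.46 and 0.91 to 0.97 with a median split. A continuous predictor gives somewhat more, still below 0.80 in the first two rows.

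All of this rests on the assumptions listed in the working. Smaller true effects would lower the figures by an amount that depends on the scale used to define them, so no single reduced figure is offered. The defect is in what is claimed and in how a null interaction would be read. It does not invalidate the design.

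**What to change.** In section 15.1:

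1. State that the 3-month figures in Table 2 are power for a difference in mean MADRS.
2. Give power for 8-week remission within the roughly 87 escitalopram participants, naming the effect scale, so that the undefined 0.45 is no longer needed.
3. Give power for the arm-by-tract interaction in 87 versus 43, as a range over the placebo non-remission rate and the effect size.
4. Say in advance that a non-significant interaction will not be taken as evidence of a shared drug and placebo effect, and report its estimate with a confidence interval.
5. Pre-specify a supporting linear model of week-8 MADRS with the same interaction, adjusted for baseline MADRS. Section 15.0 allows a linear model where the outcome calls for one but specifies none for week-8 MADRS. Power of about 0.7 in the first two rows is a gain, not a cure.

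Remission stays the outcome. MADRS is already collected every two weeks, so no new data are needed. The cost is a less favourable power statement and one extra regression.

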Hypothesis 1: Greater CB WML volume is associated with a) reduced resting-state connectivity of frontal, temporal, and cingulate regions and b) deficits in attention, memory and processing speed.

Hypothesis 2: Greater UF WML volume is associated with a) reduced resting state functional connectivity between frontocingulate and medial temporal regions, and b) greater depression severity and negativity bias.

Exploratory Hypothesis: Greater CB WML volume is associated with failure of anterior and posterior DMN nodes to deactivate during attentional components of the fMRI task. Greater UF WML volume is associated with greater medial temporal reactivity during affective components of the fMRI task.

Specific Aim 2: To determine whether deficits in tract structural / functional connectivity predict nonremission to antidepressant treatments and if these relationships vary based on antidepressant mechanism of action.

Hypothesis 3: Nonremission to escitalopram will be predicted by: a) greater WML volume in the CB and UF, and b) reduced resting functional connectivity between structures connected by the CB and UF. Greater WML severity and reduced functional connectivity in these tracts will not significantly predict response to placebo.

Hypothesis 4: Nonremission to bupropion will be predicted by a) greater WML volume in the UF but not CB, and b) reduced resting functional connectivity deficits between structures connected by the UF but not CB.

Exploratory Aims: **Expl. Aim 1)** To determine if specific cognitive measures may serve as markers of focal tract WML damage. **Expl. Aim 2)** To use whole-brain multimodal imaging approaches to examine how connectivity differences in other brain regions may also predict nonremission to antidepressants.

For exploratory analyses, we will also recruit 30 elders with no psychiatric history. Data from this population will help us understand whether our neural and cognitive findings in depression represent differences from what is seen in healthy aging, or whether our observations in depressed elders are within the range of normal aging. This will be important for data interpretation and planning for future projects.

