4.0 ENTRY CRITERIA

We plan to enroll a cohort of 200 individuals to meet goals of having 130 evaluable subjects. Participants will meet DSM-IV-TR criteria for MDD, single episode, recurrent, or chronic. We will not be enrolling vulnerable populations, specifically pregnant women, children, prisoners, or institutionalized individuals. We also will not enroll subjects incapable of providing their own consent. Should a potential subject present where there is a concern (either by a study clinician or staff member) about their ability to understand study procedures and provide meaningful consent, their cognitive ability and understanding will be evaluated by a study doctor. If there is any concern that the individual may be impaired, they will not be enrolled in the study. The rationale will be provided to the individual as well as his or her family members. Referrals for further evaluation, including urgent or emergent evaluation, will be made as needed and clinically warranted.

Men and women of all races / ethnicities are eligible.

Depressed Cohort:

Inclusion Criteria:

- 1) Age 60 years or older.
- 2) Current diagnosis of major depressive disorder (DSM-IV-TR), single episode, recurrent or chronic, without psychotic features, as detected by MINI and clinical exam.
- 3) Minimum MADRS score ≥ 15 .
- 4) Mini-Mental State Exam ≥ 24 .
- 5) Fluent in English.

Exclusion Criteria:

Diagnostic Issues:

- 1) Current or past diagnoses of other Axis I psychiatric disorders, except for generalized anxiety disorder (GAD) symptoms occurring during a depressive episode
- 2) History of alcohol or drug dependence or abuse in the last three years
- 3) History of developmental disorder or IQ score < 70
- 4) Presence of acute suicidal ideation, defined as a "yes" response to items 3, 4, or 5 on the C-SSRS
- 5) Acute grief (< 1 month)

Protocol Version: 2.0

Protocol Date: 04/10/2020

- 6) Current or past psychosis

Medical Issues:

- 7) Primary neurological disorder, including but not limited to dementia, stroke, brain tumors, epilepsy, Parkinson's disease, or demyelinating diseases
- 8) MRI contraindications
- 9) Any physical or intellectual disability adversely affecting ability to complete assessments
- 10) Current pregnancy or capable of becoming pregnant (defined as ability to have children [i.e., has not had a hysterectomy or bilateral oophorectomy] and is not clearly postmenopausal [> 1 year of amenorrhea])

Antidepressant Treatment Issues:

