9.6. Concomitant treatment: To enhance generalizability, most nonpsychotropic medications will be permitted. Concomitant psychotherapy will not be allowed as it is an effective treatment that contributes to remission through different mechanisms. We allow short-acting hypnotics (eszopiclone, zolpidem, or zaleplon) for sleep and lorazepam up to 2mg daily for anxiety. Hypnotics will be discouraged the day of cognitive testing.

9.7 Antidepressant Washout: If potential subjects are currently taking an antidepressant, they may need to come off that antidepressant in order to participate. In order to qualify to have the current antidepressant stopped, participants will need to have continued significant depressive symptomatology (MADRS \geq 15) despite taking a therapeutic dose of their current antidepressant for at least 6 weeks. The therapeutic dose will be drug specific, but equivalent to fluoxetine 20mg (such as sertraline 50mg or escitalopram 10mg, for example). Individuals who responded to their antidepressant and do not have this level of depressive symptom severity will not be enrolled in the study and will not be tapered off their medication. The medication taper will occur over 1-3 weeks, dependent on the drug, dose, and duration. They will be assessed with weekly telephone visits during this period to monitor for depression worsening.

9.8. Source of Study Drug: The Vanderbilt Investigational Drug Service will provide study drug for both Phase 1 and Phase 2 for all participants aside from Veterans who receive care at the VA TVHS. Veterans will receive study drug from the VA TVHS Research Pharmacy. The Vanderbilt IDS will coordinate with the VA TVHS Research Pharmacy to assure accuracy in study drug assignment for Phase 1.

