15.0 STATISTICAL CONSIDERATIONS

For **Aim 1**, inter-correlation matrices and scatter plots will be used to assess and visualize the patterns of association among the tract WML values and respective fMRI connectivity values. Multivariate analysis will be conducted using canonical correlation. Canonical correlation can accommodate more than one variable on both the independent and dependent sides of the general linear modeling equation and those variables may be either metric or nonmetric. In canonical analysis, the solution depends both on correlations among the variables in each set and on correlations among variables between sets. In a simultaneous process, underlying canonical variates (or factor loadings) comprising the WML values on the independent side will be constructed in such a way to maximize the correlations with canonical variates of the fMRI values on the dependent side. The same assumptions as those underlying multiple linear regression apply. Evaluations of normality, linearity, and homoscedasticity will be conducted, as will tests of multicollinearity and singularity of the underlying correlation matrices. Simple bivariate correlations and scatterplots will assist with describing and visually the patterns of association, canonical correlation will control for the inter-correlations among the WML and fMRI values will maximizing the correlation between the two sets. Covariates of *age, sex, and vascular risk* will be included with the WML measures. Effects of *MADRS and total brain WML volume* will also be examined. We will use a similar approach to examine how WML values are associated with clinical presentation. For Hypothesis 1, attention, memory, and processing speed scores will be on the dependent side. For Hyp. 2, BRISC and baseline MADRS scores will be on the dependent side.

For the fMRI emotional dot-probe task, we will examine how WMLs are associated with ROI activation(Exploratory Hyp). Specifically, we will examine how CB measures are associated with activity in DMN and CCN regions during the task's attentional component and how UF measures are associated with amygdala activity during the affective component. In this analysis WML measures will be on the "independent" side of the canonical correlation while fMRI activation values will be "dependent" side.

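### Table 2's power of 0.98 for baseline MADRS by right-UF lesion volume rests on pilot scores that very probably extend below 15, but the trial enrols only depressed patients with MADRS of at least 15

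*Combined protocol and SAP*

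**What the plan says.** Section 2.0 sets out the clinical part of Hypothesis 2, for greater UF WML volume, as "b) greater depression severity and negativity bias". Section 15.0 names the variables: "For Hyp. 2, BRISC and baseline MADRS scores will be on the dependent side".

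The same scale decides entry. Section 4.0, inclusion criterion 3 for the depressed cohort, is "Minimum MADRS score ≥ 15". Section 9.7 repeats the floor for people already taking an antidepressant: responders who "do not have this level of depressive symptom severity will not be enrolled in the study".

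Section 15.1, in its Aim 2 paragraph, introduces the power table: "Table 2 presents estimates for our proposed sample size using unadjusted effects of low vs. high WML values on the respective". Those effects are taken from the team's pilot work. The baseline MADRS rows, low WML against high WML, are:

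- right UF: 21.0 (12.2) against 29.5 (3.0), power 0.98
- right ATR: 17.4 (8.6) against 29.7 (9.0), power 1.00

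The Aim 1 paragraph of Section 15.1 gives separate, generic power statements for 130 participants: above 90% for associations of 0.30 or more, and 83% for an R² of 0.06. The documents do not give the pilot cohort's entry rule, its group sizes or its score distribution, and they make no allowance for the floor of 15.

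**The concern.** MADRS is both the gate into the sample and the outcome. The pilot contrast for the right UF appears to come largely from low-WML participants with low scores, who would not be eligible here. Removing them raises the low-WML mean towards the high-WML mean, so the difference to be detected shrinks. The table nevertheless presents 0.98 as the power at the trial's own sample size. If the UF-severity association comes out weak, a reader holding that figure would give the null more weight than it deserves, because range restriction alone could produce much of the weakness.

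**Working it through.** **Inputs.** From Table 2: right UF, low WML 21.0 (12.2), high WML 29.5 (3.0), power 0.98. From Section 4.0: floor of 15. From Section 15.1: N = 130. Assumptions: parentheses are SDs; alpha is two-sided 0.05; the MADRS maximum is 60; the low/high split is unknown, so several are tried.

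**Step 1: reproduce the stated figure.** Pooled SD = √((12.2² + 3.0²)/2) = √78.92 = 8.88. d = 8.5/8.88 = 0.96. With 65 per group the noncentrality is 0.957 × √(65/2) = 5.45 and power is 0.9997. With 44/43 (about the size of the escitalopram arm) power is 0.992. A power of 0.98 corresponds to about 36 per group. The table does not state its group sizes, so the match is to within 2 points. The arithmetic behind 0.98 is not in dispute.

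**Step 2: could the low-WML pilot group have respected a floor of 15?** Take the two-point distribution with all lower scores at exactly 15.

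- Right UF: share at 15 = 12.2²/(12.2² + 6.0²) = 148.84/184.84 = 0.81; the rest would score 15 + 184.84/6.0 = 45.8.
- Right ATR: share at 15 = 8.6²/(8.6² + 2.4²) = 73.96/79.72 = 0.93; the rest would score 15 + 79.72/2.4 = 48.2.

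So a floor of 15 is possible only with extreme skew. Scores below 15 are the reasonable reading, though the documents do not state it.

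**Step 3: apply the floor (normal shape, cut at 15 and 60).** a = (15 − 21.0)/12.2 = −0.492 and b = (60 − 21.0)/12.2 = 3.197. The share below 15 is 0.311 and the share kept is 0.688.

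- Mean = 21.0 + 12.2 × (0.3535 − 0.0024)/0.688 = 27.2.
- The truncated SD is 8.4.
- The high-WML group is unchanged, since 15 lies (29.5 − 15)/3.0 = 4.8 SDs below its mean.
- The difference falls from 8.5 to 2.3 points. Pooled SD = √((8.41² + 3.0²)/2) = 6.31 and d = 0.36. Noncentrality at 65/65 is 0.36 × 5.70 = 2.05, giving power 0.53.

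**Step 4: vary what is unknown.** The 14.5 cut treats scores as integers. Power is for unequal variances (Welch) at N = 130; pooled values at 65/65 differ by less than 0.005.

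| Low-group shape, cut | Share below | Mean (SD) after | Difference | 65/65 | 98 low/32 high | 32 low/98 high |
|---|---|---|---|---|---|---|
| Normal, 15 | 0.31 | 27.2 (8.4) | 2.3 | 0.527 | 0.615 | 0.307 |
| Normal, 14.5 | 0.30 | 27.0 (8.5) | 2.5 | 0.607 | 0.700 | 0.359 |
| Gamma, 15 | 0.36 | 26.8 (9.5) | 2.7 | 0.577 | 0.685 | 0.335 |
| Gamma, 14.5 | 0.34 | 26.4 (9.6) | 3.1 | 0.678 | 0.784 | 0.406 |
| Beta on 0-60, 15 | 0.365 | 28.1 (9.3) | 1.4 | 0.201 | 0.244 | 0.123 |
| Beta on 0-60, 14.5 | 0.35 | 27.8 (9.4) | 1.7 | 0.275 | 0.337 | 0.161 |

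At 44/43 the normal shape gives 0.38 to 0.44. No combination tried comes near 0.98.

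**Step 5: compare with the Aim 1 power text.** For equal groups r = d/√(d² + 4). Before truncation r = 0.957/√4.916 = 0.43. After it, under the normal shape, d of 0.36 to 0.40 gives r of 0.18 to 0.20, or R² of 0.03 to 0.04. These lie below 0.30 and 0.06. The comparison is rough, because this r is on a two-group scale and the planned analysis uses WML values.

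**Step 6: the other baseline row.** For the right ATR the same normal truncation at 15 gives 22.8 (5.6) against 30.7 (8.1): a difference of 7.9, d = 1.13, and power still about 1.00 at equal splits of 130 or 87. The loss is specific to the right-UF row.

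**The case against.** **The 0.98 is not the formal power statement for Hypothesis 2.** Aim 1 has its own text, which does not use Table 2's means. The table is introduced under Aim 2 and labelled as unadjusted and preliminary. This stands in part: nothing shows that N = 130 was derived from the UF row, and a reader who concluded that the whole sample size falls with it would be going beyond the documents. But baseline MADRS is not a remission outcome and serves only as a covariate in Aim 2, so the row can support only the severity hypothesis. The generic text does not rescue it, since the implied r after truncation is below the values assumed there.

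**The pilot data are unseen.** This also stands. Scores below 15 are inferred from a mean and SD, and the size of the loss depends on shape and split. The normal shape itself puts about 4% of the low group below zero. A narrow replacement such as 0.3-0.6 is tempting, but the same published means and SDs also give 0.78 and 0.20.

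**A symptom floor is inherent in a trial that treats current depression.** True, and the entry rule is not at issue. The point is that power should be calculated for the sample that will be enrolled.

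**Nondepressed elders join the analyses.** They must score 8 or less, but Section 15.0 adds a group term, so the association within depressed participants remains restricted.

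**Conclusion.** The stated 0.98 does not carry over to the sample this trial enrols. Applying the floor reduces the expected right-UF difference from 8.5 points to about 2-3 points under normal or gamma shapes, and to less under the beta shape. Power becomes about 0.5-0.6 at 65/65 under a normal shape, and roughly 0.2-0.8 across plausible shapes and splits, with the beta shape and uneven splits reaching 0.12. The direction is firm; the exact figure is not. It rests on reading the parentheses as SDs, on a MADRS maximum of 60, and on assumed shapes and splits.

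The reach is limited to one Table 2 row and one of the two clinical outcomes of one Aim 1 hypothesis. The right-ATR row keeps its power. The connectivity part of Hypothesis 2, the BRISC outcome and the Aim 2 remission analyses are not shown to be affected.

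Three stronger readings are not supported. A reader might infer that the floor cuts only low-WML participants; that holds for the right UF, but about 5% of the high-WML right-ATR group would also fall below 15 under a normal shape. A reader might infer that the trial will return a null; that is a risk, not a prediction. And a reader might infer that a null would carry no evidence against the hypothesis. It would carry some, for eligible depressed patients, within the limits of its precision and of the range restriction.

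**What to change.** 1. Recompute the right-UF baseline MADRS row of Table 2 using only pilot participants with MADRS of at least 15. Replace 0.98 with that result and state the group sizes used. If this cannot be done, withdraw the row as support for the severity part of Hypothesis 2.
2. Add a sentence to Section 15.0: the UF-severity association is estimated in a sample restricted on MADRS, so it is attenuated, and a null must be read with its confidence interval and the reduced power.
3. Optionally, report baseline QIDS-SR16 alongside MADRS. Section 8.1.a already lists it as a secondary severity measure. It is only partly free of the restriction, because it correlates with MADRS, and it adds one more dependent variable.

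The cost is a recalculation on existing pilot data and a short change to the text; enrolment and procedures do not change. The downside is a less favourable power figure for this hypothesis.
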